**A Randomized Controlled Trial Testing the Efficacy of Humor and Framing in Messaging to
Correct Misperceptions About COVID-19 Vaccines**

NCT05085613

IRB approved 8/4/2021

Abstract: More than one million people in the United States have died from COVID-19-related complications.¹ Despite vaccine availability, as of June 2022, approximately 9% of the eligible adult population hadn't received a single dose of the COVID vaccine, and in some states rates of having gotten at least one dose are as low as 71%.¹ The unvaccinated and under-vaccinated remain more susceptible to severe outcomes from COVID, including hospitalization and death.² Vaccine hesitancy is partially driven by misperceptions, including the belief that they are not safe, and not effective.³ Identifying strategies to correct this misperception may potentially increase vaccine uptake. Correcting misperceptions, however, is not a straightforward process, and often fails due to the Continued Influence Effect (CIE). The CIE occurs when misinformation in memory continues to influence inferences and decisions even after correction, which presents a barrier to misperception correction.⁴ Additional communication strategies can also be considered. As Conservatives have lower rates of vaccination,⁵ framing the consequence of vaccination to resonate with conservative values like freedom (i.e. If you get vaccinated, you'll have the freedom to engage in social activities) and economic recovery (i.e. If you get vaccinated, businesses can stay open and Americans can keep working and supporting their families)^{6,7} has the potential to increase message efficacy and reduce reactance by aligning the message with the readers values.^{8,9} Likewise, there is evidence that humor can improve message efficacy. Humor can increase attention, message liking, and can produce positive affect that may reduce reactance and motivate effortful message processing.¹⁰⁻¹²

Objectives: This study tests the efficacy of adding a freedom consequent frame, an economic recovery consequent frame, or humor to a coherent corrective message in a randomized controlled experiment to compare their efficacy to a message that is coherent, but does not include a frame or humor. Outcomes include beliefs that FDA-authorized vaccines are safe and effective (e.g. an indicator of message recall and acceptance due to surface updating) and inferential beliefs about the safety and effectiveness of other vaccines that either did or did not receive FDA authorization. These related concepts test whether participants updated their mental models of FDA review and can use these updated models to make inferences when asked about the safety and effectiveness of other vaccines (e.g. an indicator of updated conceptual understanding via global updating).

Background: The persistence of misperception has been noted in other disciplines, including cognitive psychology and political science. Many experiments in these fields have demonstrated that exposure to corrective information can elicit correct recall of the corrective information, however, misinformation is often still used to make inferences about related topics, which has come to be known as the Continued Influence Effect (CIE).^{4,13,14} It has been theorized that, when presented with corrective messaging, individuals may engage in 'surface updating' (the individual updates only the specific misperception addressed in the message), but fail to engage in 'global updating' (fully integrating information into beliefs so it can be applied via inferential reasoning and behavioral decisions).^{4,13,14} Thus, it is possible that after exposure to corrective information about nicotine, an individual could accurately state that nicotine is not the main cancer-causing constituent in tobacco (surface updating), yet fail to accurately characterize the relative harm of a non-combustible nicotine-containing product when compared to a combustible cigarette if that product was not discussed in the message (global updating).¹⁵ This study combines typical corrective strategies with framing and humor to assess effects on misperceptions about the COVID vaccines,

Study Procedures

Participants were recruited online using Amazon Mechanical Turk. After clicking on the tasks, participants first consented to answering questions on a screening questionnaire to determine eligibility. Eligible participants then read an informed consent for the experiment. After agreeing to participate, participants were asked questions about their sociodemographic characteristics, beliefs, behaviors, and

behavioral intentions about the COVID vaccines. Participants were then randomized to view one of four messages using a 1:1:1:1 ratio using the “evenly present elements” option in Qualtrics. All messages had similar information about the COVID vaccines safety and effectiveness. One message had an economic recovery frame, one had a freedom frame, one included humor, and the control didn’t include a frame or humor. As randomization was conducted in Qualtrics, both experimenters and participants were blinded to randomization. After message exposure, participants answered questions about the message and their beliefs and intentions to get a COVID vaccine. The survey took between 10-15 mins to complete. The study protocol was approved by the Institutional Review Board at the Johns Hopkins Bloomberg School of Public Health on August 4, 2021 (IRB00015120). No participants were removed while the study was ongoing, but responses that showed signs of being repeat responders or bots (according to metrics from survey platform Qualtrics) were later dropped from analysis.

Inclusion Criteria

1. 21 years of age or older
2. Not yet received a COVID vaccine
3. Not completed the cognitive interview during message development
4. Rated agreement with the following statement as less than or equal to 50 out of 100: “The FDA has only authorized COVID vaccines that are safe and effective”

Exclusion Criteria

1. Under the age of 21.
2. Had already received a COVID vaccine
3. Had completed a cognitive interview during message development.
4. Rated agreement with the following statement as greater than 50 out of 100: “The FDA has only authorized COVID vaccines that are safe and effective”

Study Statistics

- a. Primary outcome variable
 1. Change in Accuracy of the Belief That FDA Authorized COVID-19 Vaccines Are Safe and Effective
 2. Accuracy of Inferential Belief That the FDA Authorized Flu Vaccine is Safe and Effective
 3. Accuracy of Inferential Belief That ResVax is Safe and Effective
 4. Change in Intention to Get a COVID-19 Vaccine

Statistical plan: Stata version 15 was used for all statistical analyses. Participant characteristics are reported as sample proportions and counts for categorical variables and median and interquartile range for continuous variables due to skewed distributions. Fisher’s exact tests were used to assess balancing across conditions by categorical variables to account for the small sample size (e.g. cell sizes with $n < 10$).⁸⁵ Non-parametric Kruskal-Wallis tests were used to assess differences in continuous variables to assess balancing by condition. Fisher’s exact test was also used to assess differences in response to manipulation check questions by condition. Kruskal-Wallis tests were used to assess differences in perceived message credibility and campaign targeted knowledge by condition. Repeated measures t-tests were used to assess the significance of an overall unadjusted change in belief that COVID vaccines are safe and effective between pre and post message exposure (H1). ANCOVAs were used to assess if there was a difference by message condition and 1. Accuracy of belief that FDA-authorized COVID vaccines are safe and effective (H2), 2. Accuracy of inferential beliefs about the safety and effectiveness of FDA-authorized flu vaccines (H3), and 3. Accuracy of inferential beliefs about the safety and effectiveness of ResVax, which did not receive FDA authorization (H4). Baseline belief that the COVID vaccines were safe and effective, race, sex, geographic region, and political affiliation were a priori included as covariates in ANCOVA 1. Race, highest educational attainment, sex, geographic region, and political affiliation were included as a priori covariates in ANCOVAs 2 and 3. Covariates were selected based on their association with vaccine

perceptions in extant literature. Message recall was not included in ANCOVAs because most participants had perfect recall, there were no differences observed in message recall by condition, and including of recall in ANCOVAs did not improve model fit. When condition was significant at $p < .05$, pairwise comparisons comparing each experimental condition (economic recovery, humor, freedom), to the control condition were made using Sidak's adjustment, which is slightly less conservative than Bonferroni and appropriate to control the type I error rate during pairwise comparisons after an ANCOVA when the sample size between groups is not equal.

Risks

- a. Risks were minimal and included boredom of discomfort from answering survey questions.
- b. To mitigate this risk, participants read in the informed consent that they were free to skip any questions they didn't want to answer or quit their participation at any time.
- c. There were no unanticipated problems or deviations during data collection.

Benefits

- a. Participants did not participate directly from being in the study. Findings can help to inform what kind of messaging might be helpful to adults who were hesitant to get the COVID vaccine to help correct misperceptions and increase intention to get vaccinated.

Payment and Remuneration

- a. Participants were paid \$5.00 for completing the survey. Participants who were eligible but did not fully complete the survey were still paid.

Costs

- a. No costs were associated with participation.

References

1. Centers for Disease Control and Prevention. CDC COVID data tracker. *Cent Dis Control Prev.* Published online August 2022. <https://covid.cdc.gov/covid-data-tracker/#datatracker-home>
2. Centers for Disease Control and Prevention. Rates of laboratory-confirmed COVID-19 hospitalizations by vaccination status. *CDC COVID Data Tracker*. Published online 2022. <https://covid.cdc.gov/covid-data-tracker/#covidnet-hospitalizations-vaccination>
3. Monte L. Who are the adults not vaccinated against COVID? *US Census Bur*. Published online December 2021. <https://www.census.gov/library/stories/2021/12/who-are-the-adults-not-vaccinated-against-covid.html>

7. Harvard University. COVID-19 Vaccine Rollout across US Congressional Districts. *Geogr Insights*. Published online August 2021. <https://geographicinsights.iq.harvard.edu/vaccineuscongress>

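### Vaccination intention is one of four primary outcomes, but the Statistical plan describes no hypothesis, test or covariate set for it

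*Combined protocol and SAP*

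**What the plan says.** All references are to the combined protocol and SAP. Study Statistics, item a, lists four primary outcomes: change in belief about the authorized COVID-19 vaccines, an inferential belief about the flu vaccine, an inferential belief about ResVax, and "Change in Intention to Get a COVID-19 Vaccine".

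Study Procedures indicates that data on intention exist on both sides of the intervention. Before randomization, participants were asked about "behavioral intentions about the COVID vaccines"; after exposure, "participants answered questions about the message and their beliefs and intentions to get a COVID vaccine".

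The Statistical plan uses repeated measures t-tests to "assess the significance of an overall unadjusted change in belief that COVID vaccines are safe and effective between pre and post message exposure (H1"). It then says that "ANCOVAs were used to assess if there was a difference by message condition and 1", followed by three numbered outcomes: COVID vaccine belief (H2), flu vaccine belief (H3) and ResVax belief (H4). Covariates are named for these three models only. The other tests are Fisher's exact, for balance and manipulation checks, and Kruskal-Wallis, for balance, message credibility and campaign-targeted knowledge. Intention is not mentioned in the section.

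The Objectives do not fill the gap. They state that "Outcomes include beliefs that FDA-authorized vaccines are safe and effective" and add "inferential beliefs about the safety and effectiveness of other vaccines that either did or did not receive FDA authorization". The list is open-ended, but it names beliefs only.

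**The concern.** A primary outcome should have a stated comparison, model and adjustment set. Here one has none, and it is the outcome closest to the vaccine uptake that the Abstract gives as the motivation. The Benefits section also names raising intention as a use for the findings.

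The missing analysis cannot safely be filled in by analogy. ANCOVA 1, the nearest model, adjusts for baseline belief and not for baseline intention. It omits education, whereas ANCOVAs 2 and 3 include it, and the covariates were chosen for their link with perceptions. The scale of the intention item is not given, so a reader cannot tell whether an ANCOVA would suit it.

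Two things are at stake. If the account is followed as written, the randomized question of whether a frame or humor changes intention more than the control message goes unanswered for a declared primary outcome. If an intention result appears later without a dated specification, nothing in this document lets a reader establish that its model was planned.

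**Working it through.** The plan states no figure on this point, so there is none to reproduce. The check is a one-to-one match of the primary outcome list (Study Statistics, item a) with the Statistical plan.

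| Primary outcome | Label | Test | Adjustment |
|---|---|---|---|
| 1. COVID-19 vaccine belief, change | H1 | Repeated measures t-test | None |
| | H2 | ANCOVA 1 | Baseline belief, race, sex, region, politics |
| 2. Flu vaccine belief | H3 | ANCOVA 2 | Race, education, sex, region, politics |
| 3. ResVax belief | H4 | ANCOVA 3 | As for ANCOVA 2 |
| 4. Intention, change | None | None | None |

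The counts that follow:
- Primary outcomes with a stated analysis: 3 of 4. Without one: 1 of 4 = 25%.
- Hypothesis labels on intention: 0 of 4.
- ANCOVAs on intention: 0 of 3.

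**Could text have been lost?** The labels run from H1 to H4 and the ANCOVAs from 1 to 3 without a break. Covariates are given for exactly those three models. At the one page break the sentence continues where it stopped, and there is no sign of blacked-out text. Loss in extraction is therefore an unlikely explanation.

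**What would a fourth between-message test cost?** Inputs: 0.05 per condition test (Statistical plan), three such tests now (H2 to H4), four after the addition. Assumption: independent tests, because the document gives no correlations between outcomes.
- Three tests: 1 − 0.95³ = 1 − 0.857375 = 0.1426, or 14.3%.
- Four tests: 1 − 0.95⁴ = 1 − 0.814506 = 0.1855, or 18.5%.
- Under positive correlation both figures are lower.

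The Sidak adjustment over three contrasts with control gives 1 − 0.95^(1/3) = 0.0170 per comparison. It works within one model and does not cover the set of primary outcomes. These error rates price the remedy; they do not measure the gap, which rests on the table alone.

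**The case against.** The strongest reply is that the Statistical plan is a retrospective summary and may be incomplete. It is in the past tense, and the Abstract cites figures from June 2022, well after the IRB approval of August 2021. It shows signs of having been condensed from a longer text: it cites a reference numbered 85 although the list ends at 15, and it uses the labels H1 to H4 although no hypothesis is written out. An intention analysis may therefore exist elsewhere. This stands as a limit on what can be concluded, but it does not supply the missing analysis.

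Three stronger readings are tempting and should be resisted.
- *No intention analysis was carried out, or the outcome was dropped.* The documents show only that none is described.
- *Intention was measured differently before and after the message, so change is undefined.* The two phrases in Study Procedures are one-line summaries and not item texts, and the outcome's name implies a repeated measure. It is fair to say that the item and scale are missing, but the same holds for the flu and ResVax outcomes.
- *The intention model was chosen after the data were seen.* The observed results in the Statistical plan concern message recall as a covariate in the belief models. The document contains no intention model whose timing could be questioned.

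It is also fair to say that H1 to H4 are unaffected, that the Objectives' wording leaves room for further outcomes, and that error control across outcomes is a separate matter.

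**Conclusion.** The point holds in this form: intention is declared primary and is said to have been asked before and after the message, but no hypothesis, test or covariate set is described for it. As described, the analysis gives no randomized comparison for one of four primary outcomes. This needs correction and is more than a missing detail, because the section lists models and covariates outcome by outcome and leaves this outcome out.

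The conclusion rests on reading the Statistical plan as the account of the primary analyses in this document. It assumes nothing about what was done or reported elsewhere.

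**What to change.** 1. Add to the Statistical plan one between-message model: post-message intention by condition, adjusted for baseline intention and the plan's existing covariates. State whether education is included and why, since the existing models differ on it. Use ANCOVA if the scale is roughly continuous, otherwise an ordinal or logistic model.
2. Collapse sparse covariate categories, because the plan itself notes a small sample with cells below 10.
3. Follow a significant condition effect with the same three Sidak-adjusted comparisons with control (economic recovery, freedom, humor), and report the result whatever it shows.
4. State the intention item and its scale.
5. Cite a dated specification of this analysis if there is one; otherwise label the analysis as specified after data collection.

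A pre-post test of intention, parallel to H1, is optional. It would be uncontrolled, since "All messages had similar information about the COVID vaccines safety and effectiveness" and there is no arm without a message.

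**Cost.** The work is one model on data the document says were collected, plus a few sentences. It adds one between-message test at 0.05 with no control across outcomes, a rise of about 4.3 percentage points in family-wise error (18.55% − 14.26%) under independence. An ordinal or logistic model may also be unstable in a small sample; the document gives no sample size from which to judge how likely that is.

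### Step-down Holm-Sidak would keep the 5% family-wise bound and lose no rejection compared with what reads as single-step Sidak; the power gained runs from about 0 to about 17 points, depending on which messages work

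*Combined protocol and SAP*

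**What the plan says.** Under Study Statistics, the Statistical plan describes three ANCOVAs, on the COVID vaccine belief, the flu vaccine belief and the ResVax belief: "ANCOVAs were used to assess if there was a difference by message condition". Contrasts follow only if the overall test passes ("When condition was significant at" p < .05). Then "pairwise comparisons comparing each experimental condition (economic recovery, humor, freedom), to the control condition were made" with Sidak's adjustment.

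Two reasons are given for the choice. It is "which is slightly less conservative than Bonferroni and appropriate to control the type I error rate during pairwise comparisons after an ANCOVA", and it is suitable "when the sample size between groups is not equal". No step-down rule is named. Under Study Procedures, "Participants were then randomized to view one of four messages using a 1:1:1:1 ratio", so roughly equal arms were intended. The document gives no analysed arm sizes, effect size, standard deviation or power.

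**The concern.** The Objectives section sets out to compare each addition (freedom frame, economic frame, humor) with the plain message. The three contrasts are what identify the messages that work.

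Single-step Sidak holds each contrast to the same strict level whatever the other two show. Once one message has truly beaten control, at most two null hypotheses can still be true, and protecting all three at the three-comparison level is stricter than a 5% family-wise bound requires. The cost falls on the second and third effective message.

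The reason about unequal groups does not favor the single-step version. Neither single-step nor step-down Sidak depends on arm sizes.

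**Working it through.** **Inputs.** From the Statistical plan: three contrasts per ANCOVA and an omnibus gate at 0.05. From Study Procedures: 1:1:1:1 allocation, so contrasts sharing the control have correlation 0.5 with equal arms. Assumed: a 5% family-wise level for the contrasts (inferred from the gate) and two-sided tests (the plan tests for a difference). Also assumed: 100 per arm, and effects in units of the residual SD. The plan has no power figure to reproduce.

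**1. Thresholds.**
- Bonferroni: 0.05/3 = 0.01667.
- Single-step Sidak: 1 - 0.95^(1/3) = 0.01695 for all three contrasts.
- Holm-Sidak on ordered p-values: 0.01695, then 1 - 0.95^(1/2) = 0.02532, then 0.05.

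The step from 0.01667 to 0.01695 fits the plan's word "slightly"; a rule rising to 0.05 would not. Single-step is therefore the natural reading, although it is inferred.

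**2. No rejection is lost.** The first step-down threshold equals the single-step one and the later ones are larger. Any set of p-values at or below 0.01695 is rejected under both rules. This needs no assumption about sample size or effect. It does not hold for ordinary Holm, which starts at 0.01667.

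**3. The error bound is the same.** Let m true nulls remain. When the first false rejection occurs, at least m hypotheses are still untested, so the threshold is at most 1 - 0.95^(1/m). By the Sidak inequality for two-sided tests, the chance that any of the m p-values falls below this is at most 5%. The gate can only remove rejections.

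**4. Actual error differs within that bound.** Under single-step Sidak the ceiling is 1.7% with one true null and 1 - 0.95^(2/3) = 3.4% with two. Under Holm-Sidak it is 5% in both cases.

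**5. Power by simulation.** Four arms of 100, pooled variance on 396 df, gate applied, 400,000 trials per row. At 0.4 SD the expected z is 0.4 × √(100/2) = 2.83. Each cell shows single-step → Holm-Sidak, in percent.

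| True effects (SD) | Power per effective message | All effective messages detected | Any ineffective message declared |
|---|---|---|---|
| 0.2, 0.2, 0.2 | 14.0 → 16.7 | 3.6 → 8.4 | none to declare |
| 0.4, 0.4, 0.4 | 65.2 → 72.7 | 42.7 → 60.0 | none to declare |
| 0.5, 0.5, 0.5 | 86.8 → 91.8 | 73.2 → 85.6 | none to declare |
| 0.6, 0.6, 0.6 | 96.6 → 98.4 | 91.9 → 96.8 | none to declare |
| 0.4, 0.4, 0 | 66.4 → 69.6 | 51.7 → 58.0 | 1.7 → 3.5 |
| 0.4, 0, 0 | 65.2 → 65.3 | same as per message | 3.1 → 4.0 |
| 0.8, 0.8, 0 | above 99.9 for both | 99.9 for both | 1.7 → 5.0 |
| 0.8, 0, 0 | above 99.9 for both | same as per message | 3.2 → 4.7 |

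A moderate message (expected z of 2) beside two very strong ones (z of 6) goes from 34.9% to 51.7%, a gain of about 17 points. Power to detect at least one message is 83.4% under both rules with three effects of 0.4 SD. No single-step rejection was lost in any run.

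**6. Sensitivity.** With three equal effects at an expected z of 2.8, the gains were 7.5 to 7.8 points per message and 17.2 to 17.6 for all three at 10, 25 and 50 per arm. With arm weights from 0.8 to 1.2 they were about 6 to 9 and 16 to 18 points.

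**The case against.** The case for leaving the plan alone has several parts.

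- *The method is standard and valid, and the hypotheses do not depend on it.* H2 to H4 ask whether there is a difference by message condition, which the omnibus ANCOVA answers. No section makes detecting all three messages an aim. This stands, and limits the point to identifying individual messages.
- *The gain is not free.* A reader might infer that single-step Sidak buys no extra protection. That is wrong: both rules share the 5% bound, but single-step has lower actual error when only some messages work (1.7% against about 3.5% with two effective at 0.4 SD). The plan states no adjustment across the three ANCOVAs, so the increase can arise in each. Single-step also has simple matching simultaneous intervals, although the plan mentions none.
- *The size depends on the scenario.* Three equal effects of 0.4 SD with 100 per arm lie near the peak for equal effects. A reader might take 8 points per message and 17 for all three as the plan's loss, or as ceilings. The documents support neither, since they give no sample size or effect.
- *Holm-Sidak also ignores the shared-control correlation.* True. Step-down Dunnett uses it, but is a different procedure with slightly different power.
- *It may be too late.* The plan is in the past tense and already reports that recall did not differ by condition. A switch to a more liberal rule after seeing results is post hoc.

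None of this removes the central fact: under the same family-wise bound, Holm-Sidak rejects everything that single-step Sidak rejects, and sometimes more.

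**Conclusion.** The point holds as an efficiency improvement. A reader might infer that the planned contrasts fail to control the type I error or that Sidak was the wrong method; the document supports neither, and its claim to be slightly less conservative than Bonferroni is correct.

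That no rejection is lost, and that the 5% bound is kept, follow exactly from the thresholds. The size is conditional. With 100 per arm, the gate kept and three equal effects, the gain per message is about 3 points at 0.2 SD, 7.5 at 0.4 SD, 5 at 0.5 SD and 2 at 0.6 SD. With two effective messages at 0.4 SD it is about 3 points each and 6 for detecting both. With one it is about 0, and the chance of finding at least one is essentially unchanged. The largest gain for a single message, about 17 points, goes to a moderate message beside two strong ones. These figures rest on two-sided tests and on reading the plan as single-step.

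**What to change.** In the Statistical plan, for ANCOVAs 1 to 3, replace Sidak's adjustment by Holm-Sidak: order the three message-versus-control p-values and test the smallest at 1 - 0.95^(1/3) = 0.01695, the next at 1 - 0.95^(1/2) = 0.02532 and the largest at 0.05, stopping at the first failure. The omnibus gate can stay. Show the three estimates with single-step Sidak intervals beside the tests, and say that the intervals do not match the step-down decisions exactly. Step-down Dunnett, using the fitted covariance of the contrasts, is an alternative.

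If results have already been seen, keep the planned single-step result as the planned analysis and report the step-down result beside it, labelled post hoc.

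The change costs one sentence and a re-sort of three p-values per model, with no new data. The statistical price is the loss of simple matching intervals and actual error closer to 5% when only some messages work (up to 5.0% with two strong effects).
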